**Study Title: Novel Gallium 68 Citrate Imaging in Orthopedic Infections.**

**Principal Investigator: [name]**

**Study Site: Rutgers New Jersey Medical School**

**1. Purpose/Specific Aims:**

The purpose of the current study is to demonstrate the feasibility and evaluate the accuracy of Gallium (Ga)-citrate positron emission tomography/computed tomography (PET/CT) in diagnosing prosthetic joint infection and compare it with fluorine-fluorodeoxyglucose-positron emission tomography/computed tomography (FDG-PET/CT). We expect that Ga-citrate PET/CT will serve as a novel molecular-based sensitive functional imaging modality superior to FDG-PET/CT. We intend to translate the results of this preliminary study to fuel larger studies in the utility of Ga-citrate PET/CT to evaluate prosthesis complications, where current available imaging techniques are challenging.

**2. Background and Significance**

**Epidemiology:**

A total of 4.5 and 6.7 million people in the United States are currently living with an artificial hip or knee. With aging of the population, and increased obesity and longevity, this number is likely to increase in the coming decades and will create significant challenges for management of long-term complications (1). The local complications of joint replacement include infection, instability and dislocation, aseptic loosening and periprosthetic fracture. Periprosthetic infection, the most devastating complication of joint replacement, is associated with significant morbidity and cost. The infection rates following primary implantation and revision surgery are approximately 1% and 3% for hip prostheses and 2% and 5% for knee prostheses, respectively (2, 3). The most common complication, on the other hand, is aseptic loosening which is most often caused by wear of the prosthetic components. For hip replacement, the risk of aseptic loosening leading to revision total hip arthroplasty is about 1 percent per year (4). It is crucial to differentiate prosthetic joint infection from aseptic loosening for appropriate patient management. The treatment for prosthesis infection generally involves both systemic antibiotics for an extended period and exchange arthroplasty in one or two stages, whereas aseptic loosening usually requires a single revision arthroplasty (5, 6).

Physical examination, laboratory tests, radiography and joint aspiration used to diagnose prosthesis infection are insensitive and/or nonspecific. Evaluation of prosthetic joint with morphologic imaging such as CT or MRI has been plagued by poor differentiation between infection and aseptic inflammation/loosening. These modalities are also hampered by artifacts produced by the prosthetic devices themselves (2). Functional modalities have the ability to detect infection when morphologic imaging is nonspecific (2, 7). Of these modalities, promising data exist

supporting combined leukocyte–marrow scintigraphy, 67Gallium (67Ga)-citrate imaging and 18fluorine-fluorodeoxyglucose-positron emission tomography (FDG-PET).

## Current Diagnostic Techniques:

### **Combined leukocyte–marrow scintigraphy:**

Combined 111Indium-labelled leucocyte-99mTechnetium-sulphur colloid marrow scintigraphy achieves a high diagnostic accuracy and is currently considered as the imaging modality of choice for diagnosing periprosthetic infection. However, combined leukocyte–marrow scintigraphy is time-consuming, labor-intensive, not widely available, and potentially hazardous because of direct handling of blood products (8).

### **F-FDG-PET:**

FDG acts as a glucose analog and is taken up by metabolically active cells, namely leucocytes, neutrophilic granulocytes, and macrophages because of increased glucose metabolism and expression of glucose transporters in these cells. In the case of infection, it is also taken up by bacteria present in the infected tissue (9-12). This increased FDG uptake makes local detection of bacterial infections possible. Although FDG PET/CT has high diagnostic sensitivity to detect prosthetic joint infection, its specificity is low, that is, it fails to differentiate between prosthesis infection and aseptic loosening (7, 8, 10, 13-20). The presence of periprosthetic FDG uptake in a non-infected prosthesis can be explained by altered marrow distribution secondary to the placement of an orthopaedic prosthesis (15) and an immunological reaction to wear-induced polyethylene and metal particles released from the prosthesis inlay (7).

### **Ga-citrate Imaging:**

Gallium-67 (67Ga) is a group IIIb transition metal, similar to the ferric ion in terms of its atomic radius, charge, and the inorganic complexes it forms. The uptake mechanisms of radiogallium are not fully understood (12, 21). The most generally accepted theory is that it may enter the cells by means of binding with circulating transferrin and use of transferrin receptors, and locally it may bind to lactoferrin produced by leucocytes and siderophores produced by infecting micro-organisms themselves (22-24). Another uptake mechanism may involve direct uptake of gallium by infective organisms, an occurrence that has been proven in vitro. Microorganisms grown in an iron-deficient environment produce siderophores that have an extraordinary binding affinity for gallium as well as iron. Because of little free iron present in most tissues, it is assumed that pathogenic microorganisms produce siderophores, and the siderophore–gallium complex is presumably then transported directly into the microorganism (25). Historically, 67Ga has been successfully implemented as an infection-detecting tracer in imaging of bone infections (21). However, the clinical application of 67Ga scintigraphy has been compromised due to several factors. The limited injectable activity (due to the long half-life of 78 hours) and the wide spectrum of gammas emitted by 67Ga-citrate reduce image quality and resolution. 67Ga-citrate is a cyclotron produced isotope and must be purchased commercially (21).

### **Novel Ga-citrate PET/CT:**

Gallium-68 (68Ga) is a positron-emitting cyclotron-independent radionuclide with a short half-life of 68 min. This radionuclide has been previously applied in labelling of oligonucleotides and peptides for PET imaging. 68Ga-citrate PET/CT scanning may overcome the shortcomings of 67Ga-citrate and FDG PET scanning. 68Ga-citrate has a similar mechanism of uptake and localization in the human body as 67Ga-citrate. However, as a different isotope of gallium, 68Ga-

citrate isotope presents many advantages over  $^{67}\text{Ga}$ -citrate in its use in the diagnostic work-up and management of patients with bone infection. First,  $^{68}\text{Ga}$ -citrate is a positron emitter, lending to higher resolution imaging over gamma emitters like  $^{67}\text{Ga}$ -citrate. Second, the half-life of  $^{68}\text{Ga}$  is much shorter than that of  $^{67}\text{Ga}$  (only 68 minutes), allowing patients to be given higher tracer doses and to be discharged almost free of the radioactivity. Third, the uptake phase is short, as is the whole-body image acquisition, allowing a shorter imaging time. Fourth, due to shorter half-life of  $^{68}\text{Ga}$ -citrate, there is significantly less radiation burden to patient compared to  $^{67}\text{Ga}$ -citrate. Recently, one of the commercial radiopharmacy in our area has housed Gallium generator and has promised us to deliver Gallium 68 Citrate. We recently received funding from Radiological Society of North America to assess utility of Gallium 68 Citrate in hepatocellular carcinoma patients. To our knowledge, we will be the only facility in United States pursuing such research.

### **Preliminary Studies:**

Gallium labeled radiotracers are extensively researched in Europe, Asia and Africa. However, research in this area in United States is lagging behind due to lack of commercially available generator. In preliminary studies,  $^{68}\text{Ga}$ -citrate PET/CT has been successful to identify soft tissue cellulitis and abscess in humans and osteomyelitis in animal models (21). In animal models of *Staphylococcus aureus* infection, Kumar et al demonstrated avid uptake of  $^{68}\text{Ga}$ -citrate at infected lesions as early as 5 min following injection. Despite concomitant decrease in cardiac blood pool activity, the radiotracer uptake continued to increase for up to 6 h post injection (26).  $^{68}\text{Ga}$ -citrate PET/CT has been shown to be superior to FDG PET in differentiating early bone healing from osteomyelitis in rats (12). To the best of our knowledge, there is only a single human study from Italy aiming to evaluate the efficacy of  $^{68}\text{Ga}$ -citrate PET/CT in patients with acute osteomyelitis, chronic osteomyelitis, or diskitis (27). Although a small number of patients (4 of 31) were found to have false-positive scans, the authors reported a sensitivity of 100%, a specificity of 76%, and overall accuracy of 90% in identifying these patients' sites of infection. However, regarding periprosthetic infection, their study was limited due to availability of only 7 patients with bone implants (not necessarily prosthesis) and lack of comparison with FDG PET/CT. With this background, we aim to demonstrate the feasibility and evaluate the accuracy of  $^{68}\text{Ga}$ -citrate PET/CT in diagnosing prosthetic joint infection, and compare the results with those of FDG PET for the first time.

### **3. Research Design and Methods:**

In the proposed study, our aim is to evaluate the uptake of  $^{68}\text{Ga}$ -citrate in patients with failed joint prosthesis and compare it with that of conventional  $^{18}\text{F}$ -FDG PET/CT scan. To our knowledge, ours is the first such study attempting this assessment in human. We will perform PET/CT scan with  $^{68}\text{Gallium}$  citrate and  $^{18}\text{F}$ -FDG in 17 subjects with failed hip or knee arthroplasty prosthesis. Both  $^{68}\text{Gallium}$  citrate and  $^{18}\text{F}$ -FDG scans, done within 24-48 hours from each other, will be performed within 4 weeks before surgical evaluation/revision of the hardware.

Rationale for selecting 4-week interval before surgical evaluation is that in the case of periprosthetic infection, continued antibiotic therapy may affect the results of tissue histology/culture.

### **Sample Size: 17 subjects**

**Subjects:** The study subjects will be a sample of patients more than 6 months after knee or hip replacement who present with joint pain to our orthopedic and/or infectious disease clinics. Seventeen consecutive subjects with radiographic findings concerning for prosthetic joint infection or aseptic loosening who will be going under surgical evaluation for a final tissue diagnosis within the next 4 weeks will be included in the study. If needed, we may also include patients with other forms of orthopedic hardware into the study.

University Hospital and Rutgers New Jersey Medical School (NJMS) serve as a high-volume regional care center for patients with complicated bone and joint infections. As a Level 1 Trauma Center for northern New Jersey, there is expertise in the management of post-traumatic neurosurgical and orthopedic infections, and in particular, chronic osteomyelitis and prosthetic device-related infections. Our facility cares for patients through a multidisciplinary approach with close collaborations across services including radiology and nuclear medicine, orthopedic and infectious diseases. The Division of Infectious Diseases has a designated Orthopedic Infectious Diseases Consult Service at University Hospital with two Faculty members specializing in the treatment of these infections. They provide in-hospital consultation and management with outpatient follow up, including management of patients in subacute care facilities and those receiving prolonged home antimicrobials. The service sees approximately 200 new patients annually. Therefore, it is expected that the 17 subjects needed for this protocol should be easily recruited within 12 months. As we already have resources set up to pursue Gallium 68 Citrate research, we believe that our center will be ideal location to pursue utility of this novel radiotracer in orthopedic infections.

#### ***Inclusion Criteria:***

- Non-draining, swollen and painful joint prosthesis
- At least 6 months after joint replacement.
- Elevated ESR and CRP levels
- Pending surgical evaluation and tissue sampling within the next 4 week to differentiate between infection and aseptic loosening.

#### ***Exclusion Criteria:***

- Pregnant or breast-feeding women.
- Inability to consent.
- Known or suspected hypersensitivity to metals or gallium.
- Drainage from the joint
- Active inflammatory/infectious process at any location other than prosthetic joint.
- History of HIV, lupus, rheumatoid arthritis and neutropenia

#### ***Population characteristics:***

**Record Selections:** The following data will be obtained from the charts of the index cases:

1. Age
2. Gender
3. Race/ethnicity

4. Past Medical History
5. Past surgical history
6. Current medications
7. Prior medications
8. Weight, height and body mass index
9. History of alcohol abuse
10. History of intravenous drug use
11. Evidence of HIV infection (e.g. HIV RNA/DNA PCR, Western blot, viral load)
12. History of any other joint, connective tissue or systemic inflammatory diseases (e.g. systemic lupus erythematosus, sarcoidosis, amyloidosis)
13. Joint replacement postoperative course
14. White blood cell count
15. Erythrocyte sedimentation rate
16. C-reactive protein level
17. Histopathology for any biopsied joint/bone tissue
18. Pre and postoperative CT/MRI

### ***Imaging Protocol:***

The PI, [name] has obtained investigation new drug license from FDA for the investigational compound, Ga-citrate. IBA Molecular, a commercial radiopharmacy, will synthesize F-FDG and Ga-citrate according to the method described in the literature (28) and deliver to our facility in unit doses. Combined PET/CT imaging with both radiotracers will be performed using the Discovery LS scanner (GE Medical Systems, Waukesha, WI) within 4 weeks before surgical evaluation.

**Gallium Citrate PET/CT scan:** Approximately 5 mCi of Ga-citrate will be administered intravenously. Whole body PET/CT scan will be performed after 60 minutes of uptake phase. Positron emission data will be acquired for two sets, one starting from vertex to mid-thigh level and the second from pelvis to toes. Not being much higher in terms of radiation, we opted to image the entire body to include the area of interest, investigate the biodistribution of the radiotracer and look for other foci of infection, such as in case of multifocal osteomyelitis.

**FDG PET/CT scan:** Subjects will undergo FDG PET/CT scan using the same imaging parameters either on the same day or within the next 24-48 hours. The IBA Molecular radiopharmacy will synthesize F-FDG and deliver to our facility in unit doses. The subjects will be requested to fast for a minimum of 4 h prior to PET acquisition. After confirmation of a blood glucose level  $\leq$ 200 mg/dl, technologists will establish the intravenous access and the subject will receive approximately 10 mCi of F-FDG intravenously. The subject will be placed in uptake room for 60 minutes to allow for optimal localization of the compound. The subjects will be requested to void prior to administration of FDG and again prior to image acquisition. Whole body PET/CT scan will be performed after 60 minutes of uptake phase using similar imaging parameters as described above.

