### **Image Acquisition Parameters:**

**Gallium PET/CT:**  $^{68}\text{Ga}$ -citrate will be synthesized according to the method described in the literature (28). IBA Molecular, a commercial radiopharmacy, will obtain a  $^{68}\text{Ge}/^{68}\text{Ga}$  generator that is produced by ITG Isotope Products. The IBA Molecular radiopharmacy will synthesize  $^{68}\text{Ga}$ -citrate and deliver to our facility in unit doses. Technologists will establish the intravenous access and the subject will receive 5 mCi of  $^{68}\text{Ga}$ -citrate intravenously. The subject will be placed in uptake room for 60 minutes to allow for optimal localization of investigational compound. Whole body PET/CT scan will be performed after 60 minutes of uptake phase.

Combined PET/CT imaging will be performed using the Discovery LS scanner (GE Medical Systems, Waukesha, WI). The CT scanner portion of the Discovery LS consists of a multi-detector helical CT (GE Lightspeed Plus, Waukesha, WI).

- Low dose CT scan will be performed followed by positron emission scan.
- CT imaging parameters will be as follows for a 6 to 7 bed position acquisition: 140 kVp, 80 mA, 0.8 s per CT rotation, pitch of 6, 22.5 mm/s table speed. CT thickness will be 5 mm.
- Positron emission data will be acquired for two sets of 6 positions, one starting from vertex to mid-thigh level and the second from pelvis to toes. Emission data will be acquired for 5 minutes for each bed position.
- PET images will be reconstructed using CT for attenuation correction with the ordered subset expectation maximization (OSEM) algorithm.

**FDG PET/CT:** Subjects will undergo FDG PET/CT scan using the same imaging parameters either on the same day or within the next 24-48 hours. The IBA Molecular radiopharmacy will synthesize F-FDG and deliver to our facility in unit doses. The subjects will be requested to fast for a minimum of 4 h prior to PET acquisition. After confirmation of a blood glucose level  $\leq$ 200 mg/dl, technologists will establish the intravenous access and the subject will receive approximately 10 mCi of F-FDG intravenously. The subject will be placed in uptake room for 60 minutes to allow for optimal localization of the compound. subjects will be requested to void prior to administration of 18FDG and again prior to image acquisition. Whole body PET/CT scan will be performed after 60 minutes of uptake phase using similar imaging parameters as described above.

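### The Ga-to-FDG scan interval is worded ambiguously, and same-day scanning has no stated gap, order or handling of residual activity

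*Protocol*

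**What the plan says.** Protocol section 3 (Research Design and Methods) describes the Ga and FDG scans as "done within 24-48 hours from each other" and does not mention same-day scanning. Two later parts of the same section, Imaging Protocol and Image Acquisition Parameters, place the FDG scan "either on the same day or within the next 24-48 hours". The word next implies that Ga comes first, but no sentence fixes the order. No section sets a minimum same-day gap, a check for residual activity or a correction, and the SAP does not mention the interval.

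The Background describes 68Ga as a "positron-emitting cyclotron-independent radionuclide with a short half-life of 68 min" but draws no waiting rule from that. Both tracers are imaged on the same scanner after the same uptake time.

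The planned Ga-versus-FDG comparisons (Protocol section 4; SAP) cover mean SUV, maximum SUV, target-to-background ratio (TBR), accuracy measures, and kappa. A region counts as positive when its TBR is 2.0 or more.

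**The concern.** PET registers annihilation photons, which look the same whichever nuclide emitted the positron. Any 68Ga still present during the FDG scan is therefore counted as FDG. Under the same-day option the FDG measurement contains a contribution from the tracer it is being compared with, and its size depends on a gap that the plan leaves open. Same-day and next-day subjects would then be pooled although their FDG values are not measured alike. With 17 subjects and a fixed cut-off, a systematic shift in one arm of a paired comparison should be ruled out or at least examined, and the plan does neither.

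**Working it through.** The documents give no residual-activity figure, so there is nothing to reproduce. The size follows from the Protocol's own settings plus one outside constant.

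**Inputs from the Protocol**
- 68Ga half-life 68 min (Background).
- Ga activity: "the subject will receive 5 mCi of" tracer (Image Acquisition Parameters).
- FDG activity: "the subject will receive approximately 10 mCi of" tracer (Imaging Protocol).
- Uptake time, both tracers: "Whole body PET/CT scan will be performed after 60 minutes of uptake phase".
- Emission time: "Positron emission data will be acquired for two sets of 6 positions" at 5 min each, so 12 x 5 = 60 min. The Ga scan ends no earlier than 60 + 60 = 120 min after Ga injection.

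**Assumptions not in the documents:** 18F half-life 110 min (108 also tried); positron yield of 68Ga relative to 18F 1.0 (0.92 also tried); illustrative SUV and TBR values; 68Ga distribution unchanged between the scans.

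**Residual share, Ga first.** Let g be the extra gap between the end of the Ga scan and FDG injection, and s the time from FDG injection (60 to 120 min during emission). Then r = [5 x 2^(-(120 + g + s)/68)] / [10 x 2^(-s/110)]. At g = 0:
- scan start: 0.798/6.85 = 11.6%
- scan end: 0.433/4.69 = 9.2%

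| Extra gap | r at FDG scan start | r at scan end |
|---|---|---|
| 0 | 11.6% | 9.2% |
| 1 h | 6.3% | 5.0% |
| 2 h | 3.4% | 2.7% |
| 4 h | 1.0% | 0.8% |

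Varying half-life and yield over the stated ranges gives 10.7-11.7% at scan start and 8.5-9.4% at scan end for g = 0. With 24 h between injections, 5 x 2^(-1440/68) is about 0.000002 mCi, which is nil.

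**Effect on SUV.** Measured FDG SUV = SUV_FDG + r x SUV_Ga, so the bias is always upward. At r = 0.12:
- FDG 2, Ga 5: measured FDG 2 + 0.6 = 2.6; the gap narrows from 3.0 to 2.4.
- FDG 5, Ga 2: measured FDG 5 + 0.24 = 5.24; the gap widens from 3.0 to 3.24.

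**Effect on TBR.** Let F and G be the true FDG and Ga TBRs, and b the Ga/FDG ratio of background SUV. Measured FDG TBR = (F + r b G)/(1 + r b), a weighted average, so the F-G difference shrinks by r b/(1 + r b). With r = 0.10-0.12:
- b = 0.5: 0.05/1.05 to 0.06/1.06, about 5-6%
- b = 1: 0.10/1.10 to 0.12/1.12, about 9-11%
- b = 2: 0.20/1.20 to 0.24/1.24, about 17-19%

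**Effect on calls.** An FDG-negative region turns positive only if F is at least 2 - r b (G - 2). With b = 1 and G = 3.0, that is 1.88 at r = 0.12 and about 1.97 at r = 0.034 (2 h gap). So at r = 0.12 a true 1.95 reads (1.95 + 0.36)/1.12 = 2.06 and flips, while 1.80 reads (1.80 + 0.36)/1.12 = 1.93 and does not.

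**Reverse order.** If FDG came first on the same day with no extra gap, 18F relative to 68Ga during the Ga scan would be 3.22/2.71 = 119% at its start and 2.20/1.47 = 150% at its end. After a 4 h gap it would still be 26-33%.

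**The case against.** Four objections carry weight.

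- **Interval wording.** A reader might infer that the Protocol flatly contradicts itself. It need not: within 24-48 hours can be read as an upper limit, which includes the same day. That objection stands, so this is an ambiguity to reconcile. It does not remove the gap in the later sections, which expressly allow same-day FDG without conditions.
- **Size.** The 9-12% figure needs FDG injected the moment Ga emission ends. The post-imaging evaluation, and the voiding, glucose check and venous access before FDG, make some delay likely, and 2 h cuts the share to about 3%. This stands. The zero-gap figure is a bound, although none of those steps sets a minimum.
- **Direction.** A reader might infer that carry-over makes the tracers look alike and so always shrinks the contrast under test. That holds for TBR only. SUV is pushed up whatever the Ga value, so the SUV gap widens where FDG uptake exceeds Ga uptake. That is the pattern to be expected in aseptic loosening if FDG is the less specific tracer, as the Background argues.
- **Consequences for accuracy.** It is tempting to say that one changed call would move sensitivity or specificity by 11 to 12.5 points (1/9 to 1/8). That presumes 8 or 9 subjects per disease group. The documents give no infected/aseptic split, no share of same-day scans and no TBR distribution.

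This is also a feasibility pilot, which lowers the stakes. It still plans significance tests between the two tracers, so a known and calculable source of bias deserves a line in the plan.

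**Conclusion.** The point holds as a low-cost improvement. Followed as written, the plan permits same-day FDG scans in which 68Ga adds from about 1% (4 h gap) to 9-12% (no gap) of the 18F activity. No step in the analysis would detect or examine this. FDG mean and maximum SUV would be biased upward, and FDG TBR would be biased toward the Ga TBR, by about 9-11% of their difference at zero gap with equal background uptake. Calls would change only close to a TBR of 2.0.

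The figures rest on Ga being first, an 18F half-life of about 110 min, near-equal positron yields and an unchanged 68Ga distribution. How often results would be affected, and the effect on power, cannot be calculated from the documents. They do not support a claim that the trial's results will be biased, or biased in one overall direction. The problem is confined to same-day scanning. If the order were ever reversed, carry-over into the Ga scan would be far larger, which is why the order needs stating as well as the interval.

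**What to change.** 1. Reconcile Protocol section 3, Imaging Protocol and Image Acquisition Parameters into one statement of the interval and the scan order. Which interval applies is for the sponsor to decide.
2. In the SAP, require injection and acquisition times for both scans to be recorded. From them, calculate each subject's residual first-tracer share of activity at the time the index joint is imaged on the second scan.
3. Pre-specify a small limit for that share. Repeat all Ga-versus-FDG comparisons (mean and maximum SUV, TBR, sensitivity and specificity, kappa) without subjects above it, and report both sets of results. This is an analysis rule and does not set the scan schedule.
4. Do not rely on subtracting a decay-projected Ga signal from the FDG region. The animal work described under Preliminary Studies found lesion uptake still rising up to 6 h after injection while blood-pool activity fell, so decay alone would misstate both target and background.

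The cost is one reconciled sentence used in three places, one SAP paragraph and the recording of scan times. The data collection form is not shown, so it may already hold these times. The downside is a smaller sample in the repeat analysis, which is imprecise with 17 subjects to start from.
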